5.1.3 Subject Exclusion Criteria

The subject must be excluded from participating in the trial if the subject:

- 1. Had prior treatment of GBM with radiation and temozolomide.
- 2. Has evidence of leptomeningeal disease.
- 3. Had prior treatment with Gliadel.
- 4. Is unable (due to existent medical condition) or unwilling to have a contrast enhanced MRI of brain.
- 5. Is currently participating and receiving study therapy or has participated in a study of an investigational agent and received study therapy or used an investigational device within 4 weeks of the first dose of treatment.
- 6. Has a diagnosis of immunodeficiency or is receiving systemic steroid therapy or any other form of immunosuppressive therapy within 7 days prior to the first dose of trial treatment. Physiologic doses of steroid therapy (≤ 2 mg/day dexamethasone equivalents) by the time of first dose of treatment are allowed.
- 7. Has a known history of active TB (Bacillus Tuberculosis)
- 8. Hypersensitivity to pembrolizumab or any of its excipients.
- 9. Has had a prior anti-cancer monoclonal antibody (mAb) within 4 weeks prior to study Day 1 or who has not recovered (i.e., ≤ Grade 1 or at baseline) from adverse events due to agents administered more than 4 weeks earlier.
- 10. Has had prior chemotherapy, targeted small molecule therapy, or radiation therapy within 2 weeks prior to study Day 1 or who has not recovered (i.e., ≤ Grade 1 or at baseline) from adverse events due to a previously administered agent.

- Note: Subjects with ≤ Grade 2 neuropathy are an exception to this criterion and may qualify for the study.
- Note: If subject received major surgery, they must have recovered adequately from the toxicity and/or complications from the intervention prior to starting therapy.
- 11. Has a known additional malignancy that is progressing or requires active treatment. Exceptions include basal cell carcinoma of the skin or squamous cell carcinoma of the skin that has undergone potentially curative therapy or in situ cervical cancer.
- 12. Has active autoimmune disease that has required systemic treatment in the past 2 years (i.e. with use of disease modifying agents, corticosteroids or immunosuppressive drugs). Replacement therapy (eg., thyroxine, insulin, or physiologic corticosteroid replacement therapy for adrenal or pituitary insufficiency, etc.) is not considered a form of systemic treatment. Subjects with vitiligo or resolved childhood asthma/atopy would be an exception to this rule. Subjects that require intermittent use of bronchodilators or local steroid injections would not be excluded from the study. Subjects with hypothyroidism stable on hormone replacement or Sjorgen's syndrome will not be excluded from the study.
- 13. Has known history of, or any evidence of active, interstitial lung disease or non-infectious pneumonitis requiring corticosteroid therapy.
- 14. Has an active serious infection requiring systemic therapy.
- 15. Had major surgical procedure, open biopsy, or significant traumatic injury within 21 days prior to day 1 of treatment on study.
- 16. Has a history or current evidence of any condition, therapy, or laboratory abnormality that might confound the results of the trial, interfere with the subject's participation for the full duration of the trial, or is not in the best interest of the subject to participate, in the opinion of the treating investigator.
- 17. Has known psychiatric or substance abuse disorders that would interfere with cooperation with the requirements of the trial.
- 18. Is pregnant or breastfeeding, or expecting to conceive or father children within the projected duration of the trial, starting with the pre-screening or screening visit through 120 days after the last dose of trial treatment.
- 19. Has received prior therapy with an anti-PD-1, anti-PD-L1, or anti-PD-L2 agent.
- 20. Has a known history of Human Immunodeficiency Virus (HIV) (HIV 1/2 antibodies).
- 21. Has known active Hepatitis B (e.g., HBsAg reactive) or Hepatitis C (e.g., HCV RNA [qualitative] is detected).

22. Has received a live vaccine within 30 days of planned start of study therapy.

Note: Seasonal influenza vaccines for injection are generally inactivated flu vaccines and are allowed; however intranasal influenza vaccines (e.g., Flu-Mist®) are live attenuated vaccines, and are not allowed.

5.2 Radiation therapy

5.2.1 Dose Specifications

Radiation therapy should begin after substantial recovery from surgical resection, not more than 42 (+/- 7) days after surgery. External-beam RT to a total dose of 60 Gy will be administered in daily doses of 2 Gy, typically on a 5 days on / 2 days off schedule as appropriate for scheduling, over 6-7 weeks. RT is administered to the pre-operative tumor volume plus a 2-3 cm margin, as directed by a radiation oncologist. Radiation therapy can be administered in a local facility.

5.2.2 Radiation Therapy Adverse Events

5.2.2.1 Acute

Expected acute radiation-induced toxicities include hair loss, fatigue, and erythema or soreness of the scalp. Potential acute toxicities include nausea and vomiting as well as temporary aggravation of brain tumor symptoms such as headaches, seizures, and weakness. Reactions in the ear canals and on the ear should be observed and treated symptomatically; these reactions could result in short-term hearing impairment. Dry mouth or altered taste has been occasionally reported.

5.2.2.2 Early Delayed

Possible early delayed radiation effects include lethargy and transient worsening of existing neurological deficits occurring 1-3 months after radiotherapy treatment.

The rationale for selection of doses to be used in this trial is provided in Section 4.0 – Background and Rationale.

5.2.2.3 Late Delayed

Possible late delayed effects of radiotherapy include risk of radiation necrosis, and endocrine dysfunction. In addition, neurocognitive deficits, which could lead to mental slowing and behavioral change, are possible. Permanent hearing impairment and visual damage are rare. Cataracts can be encountered.

5.3 Trial Treatments

Treatment must begin within 21 days of registering to the trial. Treatment should also begin ≥ 3 weeks and ≤ 6 (+/1) weeks following surgery. Each cycle will consist of 12 weeks.

Dose Escalation Cohort:

Treatment will include two phases: 1) concurrent radiotherapy phase and 2) maintenance phase. Dose escalation will occur separately for concurrent radiotherapy part of treatment and maintenance part of treatment.

The dose of pembrolizumab will be 200 mg dose IV every 3 weeks. The starting dose (i.e., dose level 1) of vorinostat was 200 mg/day orally on days 1-5 every week during radiotherapy and 300 mg/day orally 1 week on 1 week off during maintenance phase, starting after completion of concurrent therapy with radiation (+/- 3 days). The dose of vorinostat during radiotherapy was reduced to 100 mg mg/day orally on days 1-5 every week due to DLT. This dose is well tolerated and is currently being expanded.

The starting dose of vorinostat during maintenance phase, beginning after completion of concurrent therapy with radiation (+/- 3 days) was 300 mg/day orally 1 week on 1 week off. The dose is escalated to 400 mg/day orally 1 week on 1 week off, as per schema in a 3+3 fashion.

Concurrent Radiotherapy Phase:

During concurrent radiotherapy phase of treatment, patients with newly diagnosed GBM will receive radiotherapy (60 Gy in 30 daily fractions) as mentioned above.

Temozolomide (75 mg/m²/day orally) will be administered daily during the course of radiotherapy as per standard of care [22]. Temozolomide will be administered continuously from Day 1 of radiotherapy to the last day of radiation at a daily oral dose of 75 mg/m2. The dose will be determined using actual body surface area (BSA) as calculated in square meters at the beginning of the concomitant treatment. The BSA will be calculated from the height obtained at the screening visit and the weight obtained at the visit immediately before the first day of treatment. The dose of temozolomide does not have to be adjusted unless there has been at least a 10% change in body weight; recalculation of dose for < 10% weight changes is allowed at the discretion of the Investigator. The daily dose will be rounded to the nearest 5 mg.

Vorinostat will be administered orally at 100, 200 or 300 mg/day dose on days 1-5 every week (based on dose level); starting on first day of radiotherapy. Safety and tolerability of vorinostat 300 mg/day dose on days 1-5 every week in combination with temozolomide (75 mg/m²/day orally) has been proven in a phase I/II trial (N0874-ABTC 0902, Alliance) by Galanis et al. 2014 [38].

Pembrolizumab will be administered as an IV intravenous infusion and will be evaluated at 200 mg. Pembrolizumab will be administered every 3 weeks (+/-3 days) starting on first day (+/- 3 days) of radiotherapy.

Table 2 summarizes the doses for pembrolizumab and vorinostat during radiotherapy part of treatment.

	Dose Escalation Schedule During Radiotherapy Phase				
Dose Level		Dose			
	Pembrolizumab	Vorinostat			
Level -1	200 mg IV every 3 weeks	100 mg/day orally on days 1-5 every week during radiotherapy			
Level 1	200 mg IV every 3 weeks	200 mg/day orally on days 1-5 every week during radiotherapy			
Level 2	200 mg IV every 3 weeks	300 mg/day orally on days 1-5 every week during radiotherapy			

Maintenance Phase:

During maintenance phase, temozolomide will start 4 weeks (+/- 7 days) after last dose of radiotherapy and will continue for 6 cycles post radiotherapy (150-200 mg/m²/day, days 1-5 every 4 +/- 1 weeks) as per standard of care [22]. As per standard of care, the starting dose for the first cycle will be 150 mg/m²/day, with a single dose escalation to 200 mg/m²/day in subsequent cycles if no temozolomide-related adverse events > Grade 2 are noted. The dose will be determined using the BSA calculated at the beginning of each treatment cycle. The BSA will be calculated from the height obtained at the screening visit and from the weight obtained at the visit immediately before each cycle. The dose of temozolomide does not have to be adjusted unless there has been at least a 10% change in body weight; recalculation of dose for < 10% weight changes is allowed at the discretion of the Investigator. The dose will also not be capped for those that are overweight. The daily dose will be rounded to the nearest 5 mg (where dosage strengths are available to accommodate rounding to 5 mg).

Vorinostat will be administered orally at 200, 300 or 400 mg/day (based on dose level) on a 1 week on 1 week off schedule for 12 months. Vorinostat will start the day after completion of radiotherapy (+ 3 days). Safety of vorinostat 400 mg/day on a 1 week on 1 week off schedule in combination with maintenance temozolomide has been shown in a phase 1 study by Lee et al. 2012 [34].

Pembrolizumab 200 mg IV will continue every 3 weeks (+/-3 days) for 12 months or 18 infusions whatever comes first

Table 3 summarizes the doses for pembrolizumab and vorinostat during maintenance part of treatment.

Table 3 Dose Escalation Schedule for Pembrolizumab and Vorinostat maintenance part of treatment.

	Dose Escalation Schedule During Maintenance Phase					
Dose Level	Dose					
	Pembrolizumab	Vorinostat				
Level -1	200 mg IV every 3 weeks	200 mg/day orally 1 week on 1 week off after radiotherapy				
Level 1	200 mg IV every 3 weeks	300 mg/day orally 1 week on 1 week off after radiotherapy				
Level 2	200 mg IV every 3 weeks	400 mg/day orally 1 week on 1 week off after radiotherapy				

In all patients, treatment with study drugs will continue until confirmed disease progression, patient refusal, patient lost to follow up, unacceptable toxicity, completion of scheduled dosing, whichever occurs first, or the study is terminated by the Sponsor (Moffitt Cancer Center).

Dose Expansion Phase:

The vorinostat doses used in the dose expansion cohort will be MTD determined from the dose escalation phase.

Definition of Maximum Tolerated Dose:

The maximum tolerated dose (MTD) is the highest dose of vorinostat in combination with pembrolizumab, temozolomide during and after radiation therapy that does not cause unacceptable toxicity in more than one of six patients at that dose level. The MTD is defined as one dose level below the highest toxic dose (i.e., the DLT dose).

Details on preparation and administration of pembrolizumab (MK-3475) are provided in the Pharmacy Manual.

5.3.1 5.3.1 Definition of Dose-Limiting Toxicity

Toxicities will be graded in severity according to the guidelines outlined in the NCI-CTCAE version 4.0. Dose limiting CNS and non-CNS toxicities will be defined differently and will be based on events that occur during the study period. In order to be declared as dose-limiting toxicity, an adverse event must be related to pembrolizumab and/or vorinostat.

A dose-limiting toxicity (DLT) will be defined as any one of the following adverse events occurring within 6 weeks from last dose of radiation therapy for radiotherapy phase and 4 weeks from the start day of maintenance dose of vorinostat [Cycle 1 Day 43 (+/-3)] for maintenance phase:

CNS toxicities:

Acute CNS toxicities (occurring \leq 30 days after completing radiation therapy):

 Any grade 3 or higher central nervous adverse events including but not limited to headache, dizziness, vertigo, new onset seizures, cerebral edema, cerebral hemorrhage, and new onset neurologic deficit.

Delayed onset CNS toxicities (occurring >30 days after completing radiation therapy):

• Any grade 3 or 4 adverse event arising within the irradiated volume including but not limited to focal neurological deficits.

Non-CNS toxicities:

- Any Grade 4 immune-related adverse event (irAE)
- Any \geq Grade 3 colitis
- Any Grade 3 or 4 non-infectious pneumonitis irrespective of duration
- Any Grade 2 pneumonitis that does not resolve to ≤ Grade 1 within 3 days of the initiation of maximal supportive care
- Any Grade 3 irAE, excluding colitis or pneumonitis, that does not downgrade to Grade 2 within 3 days after onset of the event despite optimal medical management including systemic corticosteroids or does not downgrade to ≤ Grade 1 or baseline within 14 days
- Liver transaminase elevation > 8 × upper limit of normal (ULN) or total bilirubin > 5 × ULN
- Any \geq Grade 3 non-irAE, except for the exclusions listed below

The definition excludes the following conditions:

- Grade 3 fatigue lasting ≤ 7 days
- Grade 3 endocrine disorder (thyroid, pituitary, and/or adrenal insufficiency) that is managed with or without systemic corticosteroid therapy and/or hormone replacement therapy and the subject is asymptomatic
- Grade 3 inflammatory reaction attributed to a local antitumor response (eg, inflammatory reaction)
- Concurrent vitiligo or alopecia of any AE grade

- Grade 3 infusion-related reaction (first occurrence and in the absence of steroid prophylaxis) that resolves within 6 hours with appropriate clinical management
- Grade 3 or 4 neutropenia that is not associated with fever or systemic infection that improves by at least 1 grade within 14 days. Grade 3 or Grade 4 febrile neutropenia will be a DLT regardless of duration or reversibility
- Grade 3 or 4 lymphopenia
- Grade 3 or 4 thrombocytopenia that is not associated with clinically significant bleeding that requires medical intervention, and improves by at least 1 grade within 14 days
- Isolated Grade 3 electrolyte abnormalities that are not associated with clinical signs or symptoms and are reversed with appropriate maximal medical intervention within 3 days
- Immune-related AEs are defined as AEs of an immune nature (ie, inflammatory) in the absence of a clear alternative etiology. In the absence of a clinically significant abnormality, repeat laboratory testing will be conducted to confirm significant laboratory findings prior to designation as a DLT. Laboratory abnormalities that are not deemed to be clinical significant will not be considered a DLT.

While the rules for adjudicating DLTs in the context of dose exploration are specified above, an AE not listed above may be defined as a DLT after a consultation with the sponsor and investigators, based on the emerging safety profile.

Dose escalation will be determined based on the occurrence of DLTs. For the purposes of determining whether to advance the dose levels, DLTs will be counted by patient. For all observed toxicities, subjects should be assessed for inter-current illness or other causes and treated as appropriate.

In the event of the development of any grade 3 or 4 toxicity felt to be at least possibly related to pembrolizumab, pembrolizumab will be held until resolution to grade 1 or baseline assuming that occurs within 6 weeks window. Treatment with pembrolizumab can be resumed after resolution of DLT to grade 1 or baseline except for following adverse events: Grade 4 infusion reactions, \geq Grade 3 pneumonitis, \geq Grade 3 nephritis, \geq Grade 3 colitis, increased alanine aminotransferase (ALT) or aspartate aminotransferase (AST) greater than 5 times upper limit of normal or total bilirubin greater than 3 times upper limit of normal.

Dose escalation for vorinostat will follow the standard 3+3 design. The enrollment to expansion cohort for radiotherapy phase will be delayed for 6 weeks after the completion of radiation therapy by the last patient enrolled at the MTD dose level for radiation therapy phase. The enrollment to expansion cohort for maintenance phase will be delayed for 4 weeks after the start day of maintenance dose of vorinostat [Cycle 1 Day 43 (+/-3)] by the

last patient enrolled at the MTD dose level for maintenance phase. This period will allow monitoring potential delayed toxicities. Dose escalation/de-escalation will proceed according to the following scheme.

Table 3 Dose Escalation Decision Rule

Number of Patients with DLT at a Given Dose Level	Escalation Decision Rule	
0 out of 3	Enter 3 patients at the next dose level.	
≥ 2	Dose escalation will be stopped. This dose level will be declared the maximally administered dose (highest dose administered). Three (3) additional patients will be entered at the next lowest dose level if only 3 patients were treated previously at that dose.	
1 out of 3 or ≥ 2 grade 2 CNS toxicities	 Enter at least 3 more patients at this dose level. If 0 of these 3 patients experience DLT, proceed to the expansion cohort. If 1 or more of this group suffer DLT, then dose escalation is stopped, and this dose is declared the maximally administered dose. Three (3) additional patients will be entered at the next lowest dose level if only 3 patients were treated previously at that dose. 	
≤1 out of 6 at highest dose level below the maximally administered dose	This is the dose to be used in the expanded cohort and will be considered recommended phase 2 dose.	

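### Section 5.3 gives conflicting start windows for maintenance vorinostat, one reaching back before the last radiotherapy fraction, and Section 5.3.1 labels the start day as a Cycle 1 Day 43 that a prolonged course cannot meet

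*Combined protocol and SAP*

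**What the plan says.** The start of maintenance vorinostat is described in several places.

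- Section 5.3, Dose Escalation Cohort, states the timing twice: "starting after completion of concurrent therapy with radiation (+/- 3 days" and "The starting dose of vorinostat during maintenance phase, beginning after completion of concurrent therapy with radiation (+/- 3 days) was 300 mg/day". Both carry a window on either side of completion.
- Section 5.3, Maintenance Phase: "Vorinostat will start the day after completion of radiotherapy (+ 3 days". This has a plus side only.
- The maintenance dose tables in Sections 2.2 and 5.3 label every level as given after radiotherapy.
- Section 5.3.1 sets the maintenance DLT window as "4 weeks from the start day of maintenance dose of vorinostat [Cycle 1 Day 43 (+/-3)] for maintenance phase". It uses the same bracketed day to time the hold on enrolment to the expansion cohort.

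Two further statements bear on these. Section 5.2.1 has radiotherapy given "typically on a 5 days on / 2 days off schedule as appropriate for scheduling, over 6-7 weeks", and Section 5.3.2.2.3 provides for courses longer than 7 weeks. Section 5.3 also reports: "The dose of vorinostat during radiotherapy was reduced to 100 mg mg/day orally on days 1-5 every week due to DLT". Maintenance started at 300 mg/day and is being escalated to 400 mg/day.

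**The concern.** Vorinostat is escalated separately in the two phases, and the primary objective is safety and the MTD. The maintenance start date divides exposure on one ladder from exposure on the other, and it starts the clock for the maintenance DLT window and the expansion hold.

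Two things go wrong. First, a site relying on the minus side of the dose-escalation text could give the maintenance dose while fractions are still outstanding. A site relying on the Maintenance Phase text could not. Second, a fixed calendar day cannot follow the end of a course whose length varies. If that day were used for counting, a patient with prolonged radiotherapy would be cleared for DLT before four weeks of maintenance had been observed.

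**Working it through.** **Inputs.** 30 daily fractions (Section 5.3), given on weekdays over 6-7 weeks (Section 5.2.1). Day 1 is the first day of radiotherapy. L is the day of the last fraction. Assumption: each missed fraction is made up on the next available weekday at the end of the course.

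**The plan's own figure.** 30 fractions / 5 per week = 6 weeks = 42 days, and the next day is Day 43. The bracketed day is therefore reproduced for an on-time course, and its tolerance gives Day 40-46.

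**Windows.**
- Dose-escalation text: L-3 to L+3. If the anchor is taken as the day after completion, L-2 to L+4.
- Maintenance Phase text: L+1 to L+4.
- Section 5.3.1 bracket: Day 40 to Day 46, whatever L is.

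| Course | L | Escalation text (L-3 to L+3) | Maintenance text (L+1 to L+4) | Bracket | Days in all three |
|---|---|---|---|---|---|
| Monday start, none missed | 40 | 37-43 | 41-44 | 40-46 | 41-43 |
| Tuesday-Friday start, none missed | 42 | 39-45 | 43-46 | 40-46 | 43-45 |
| Monday start, 3 missed | 45 | 42-48 | 46-49 | 40-46 | 46 |
| Monday start, 4 missed | 46 | 43-49 | 47-50 | 40-46 | none |
| Full 7 weeks | 49 | 46-52 | 50-53 | 40-46 | none |

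**Early start.** With the anchor at L, the escalation text admits L-3, L-2 and L-1 (3 days before the last fraction) and L itself. With the anchor at L+1 it admits L-2, L-1 and L (3 days on or before the last fraction). The Maintenance Phase text admits none. This holds for every course length.

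**Where the bracket fails.** The Maintenance Phase window opens at L+1 and the bracket closes at Day 46. They share no day when L+1 > 46, that is when L is 46 or later. Seven weeks is 49 days, so this lies inside the permitted range.

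**Effect on the DLT window.** Take L = 49, so vorinostat starts on Day 50-53. Four weeks counted from Day 43 close at 43 + 28 = Day 71. Observation after the first maintenance dose is 71 - 50 = 21 days down to 71 - 53 = 18 days, against 28 intended. The expansion hold would shorten in the same way.

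**Daily-dose ratios.** Against the current radiotherapy-phase dose: 300/100 = 3 and 400/100 = 4. Against the level reduced for DLT: 300/200 = 1.5 and 400/200 = 2. These compare daily doses only. The schedules differ (days 1-5 of each week against one week on, one week off), so they are not exposure ratios.

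**The case against.** The best defence is that overlap was never intended. Both parts of Section 5.3 name completion of radiotherapy as the trigger, the tables say the same, and a scheduling tolerance should not override the word 'after'. This is a fair reading of intent. But a written minus window is still a permission, and the Maintenance Phase text omits it, so the two statements remain different. The general 3-day administration allowance in Section 5.3.3 does not help: if it applies here, it adds a minus side to the Maintenance Phase rule as well.

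The second defence is that Day 43 is a gloss and not a dosing order. The words outside the bracket already count from the start day of maintenance vorinostat. That stands, and the 18-21 day figure arises only if the bracket is allowed to replace the actual start.

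Four stronger readings are tempting, and the documents do not support them.

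- A reader might infer that the start rules conflict for every patient. In an on-time course they share about three days; the bracket drops out only when radiotherapy is prolonged.
- A reader might set a Day 40 start against a Day 49 finish and infer 9-10 days of overlapping dosing. With one week on and one week off, a Day 40 start doses Days 40-46 and is then off, so at most 7 dosing days overlap. Even that requires a site to treat the bracket as the dosing rule.
- A reader might infer that a maintenance dose given during radiotherapy lies outside every level of Table 2. The daily dose at Level 2 there is 300 mg, though on another schedule. Only 400 mg/day exceeds every level's daily dose.
- A reader might infer that settling the start day would separate DLT attribution between the phases. The radiotherapy-phase window runs 6 weeks (42 days) past the last fraction. A maintenance window opening at L+1 to L+4 closes at L+29 to L+32, so it sits inside the radiotherapy-phase window even when the Maintenance Phase text is followed exactly.

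**Conclusion.** The contradiction is real but limited. The minus side in the dose-escalation text, read literally, allows about 3 days of a 300-400 mg/day maintenance dose before the last fraction. The Maintenance Phase text and the dose tables do not, and the radiotherapy-phase dose had already been halved for DLT. Separately, the Day 43 label fits an on-time course but has no day in common with the Maintenance Phase rule once radiotherapy ends on Day 46 or later. Used as the counting anchor after a Day 49 finish, it leaves 18-21 of 28 days.

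This rests on Day 1 being the first day of radiotherapy, on weekday fractions, and, for the shortened window, on counting from Day 43 itself. How often courses run to Day 46 or beyond is not stated, so the number of patients affected cannot be given. The flow chart's vorinostat row also shows a 3-day tolerance, but its layout is too broken in the available text to rely on. No sample size or confidence interval in Section 8.1 depends on this point. No view is taken on which start rule or dose is right.

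**What to change.** Reconcile Section 5.3 (both places), Section 5.3.1 (the DLT window and the expansion hold) and the flow chart to a single definition of the maintenance vorinostat start. The sponsor decides the clinical rule, and the text should say explicitly whether any maintenance-dose day may precede the last fraction and whether the general allowance in Section 5.3.3 applies to this start. Mark Day 43 as nominal or delete it, so that the four-week DLT window and the expansion hold are counted from the actual first maintenance dose, as the words outside the bracket already require.

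The cost is a wording amendment. Visit days would shift by a few days when radiotherapy is prolonged, and the expansion hold would end correspondingly later for those patients.
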